7.4.2 Concomitant Medications

The frequency of subjects receiving concomitant medications after randomization will be summarized by treatment group, medication class and drug name, using the randomized/ITT population.

7.5 Efficacy

For the primary efficacy endpoint, statistics including event rate, 95% CI for event rate, relative risk, 95% CI for relative risk and p-value will be displayed. For other endpoints, descriptive statistics including single event rate, 95% CI for single event rate, relative risk and 95% CI for relative risk will be displayed.

To construct p-values, the Cochran-Mantel-Haenszel test stratified by age groups of <10 years and ≥ 10 years old will be used at the one-sided $\alpha = 0.025$ level.

To construct descriptive statistics:

- The 95% CI for the relative risk will be computed based on Cochran-Mantel-Haenszel method stratified by age group.
- Construction of CIs for single event rates will be based on the Agresti-Coull's method

The above analyses on all the efficacy endpoints will be based on the randomized/ITT population.

7.5.1 Primary Efficacy Analysis

The primary objective is compare the effect of prophylactic oral or enteric apixaban versus no administration of systemic prophylactic anticoagulant during induction chemotherapy, on the composite endpoint of adjudicated non-fatal asymptomatic and symptomatic DVT, pulmonary embolism (PE), and CVST; and VTE-related-death during intended treatment period.

To conclude superiority of apixaban versus standard care on the primary efficacy endpoint during intended treatment period, the upper bound of the two-sided 95% CI for the relative risk (p_a/p_e) must be less than 1. This condition corresponds to a test of hypothesis $H_0: p_a = p_e$ against the alternative $H_a: p_a < p_e$ using the Mantel-Haenszel test stratified by age group (<10 years or ≥ 10 to <18 years) performed at the one-sided $\alpha = 0.025$ level. Here p_a and p_e represent the proportions of subjects with primary efficacy endpoints in the apixaban and standard care groups, respectively.

Two-sided 95% CI for the relative risk (p_a/p_e) will be reported for the primary efficacy endpoint. The p-value associated with the superiority test will also be reported.

The primary efficacy analyses will be performed based on the randomized/ITT population. Subjects with no symptomatic event and no ultrasound or echocardiogram assessment will be counted as not having an event.

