5 SAMPLE SIZE AND POWER

With a total of approximately 500 randomized subjects allocated with 1:1 ratio to the systemic thromboprophylaxis with apixaban or no systemic anticoagulant prophylaxis (control) group, there is more than 80% power to demonstrate superiority at a one-sided 0.025 level, assuming the true event rates of primary endpoint (composite of non-fatal asymptomatic and symptomatic DVT, pulmonary embolism (PE), and CVST; and VTE-related-death) are 17% and 8.5% in the control and the apixaban groups, respectively. Sample size estimation is based on Pearson's chi-square test.

Additionally, there is more than 80% power to demonstrate superiority at a one-sided 0.025 level, assuming the true event rates are 20% and 10% in the control and the apixaban groups, respectively with analyses that assume that 20% of the subjects will be excluded from the primary analysis due to either early dropout without end-of-treatment imaging evaluation or non-evaluable end-of-treatment imaging measurement in the calculation.

Randomization will be stratified by age groups as <10 years or ≥ 10 to <18 years, to reflect the major peaks of disease prevalence and risk stratification criteria for acute lymphoblastic leukemia (ALL) in children.

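### SAP 7.5.1 ties superiority to a relative-risk interval and equates it with the stratified Mantel-Haenszel test, but the usual interval is not equivalent, so one decision statistic should be named (minor)

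*SAP*

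**What the plan says.** SAP 7.5.1 gives one condition for superiority on the primary efficacy endpoint. The upper bound of the two-sided 95% interval for the relative risk (apixaban over standard care) "must be less than 1. This condition corresponds to a test of hypothesis". The test named there is the Mantel-Haenszel test stratified by age group, one-sided at 0.025. The section adds that its p-value is reported as well.

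SAP 7.5 is arranged differently. The stratified Cochran-Mantel-Haenszel (CMH) test produces the p-value at one-sided 0.025. The interval appears under descriptive statistics: "The 95% CI for the relative risk will be computed based on Cochran-Mantel-Haenszel method stratified by age group". Protocol 8.4.2 has the same arrangement and contains no rule based on the upper bound. Neither document gives a variance formula for the interval.

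SAP 5 sizes the trial on a test, not an interval: "Sample size estimation is based on Pearson's chi-square test".

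**The concern.** The CMH test uses the hypergeometric variance, computed under no treatment effect. The usual Mantel-Haenszel relative-risk interval uses a log-scale variance computed at the observed rates. One is not the inversion of the other, so the stated correspondence need not hold close to the boundary.

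This is the trial's only confirmatory decision. In a borderline case the report could show a p-value below 0.025 beside an interval that includes 1. SAP 7.5.1 would then point to the interval, while SAP 7.5 and protocol 8.4.2 treat the test as inferential.

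The tipping-point analysis in SAP 7.5.1.1 is also touched. It looks for the number of added apixaban events at which significance is lost, which is exactly where the two rules can part.

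**Working it through.** **Inputs (SAP 5).** "With a total of approximately 500 randomized subjects allocated with 1:1 ratio", so 250 per arm. Rates "are 17% and 8.5% in the control and the apixaban groups, respectively". Second scenario: "assuming the true event rates are 20% and 10% in the control and the apixaban groups, respectively", with "20% of the subjects will be excluded from the primary analysis", leaving 200 per arm. Claim: "there is more than 80% power to demonstrate superiority at a one-sided 0.025 level".

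**Step 1. The plan's power.** Pearson chi-square with pooled variance and no continuity correction; power = Φ[(difference − 1.96 × pooled SE) / unpooled SE].
- 17% versus 8.5%, 250 per arm: pooled SE = √(2 × 0.1275 × 0.8725 / 250) = 0.02983; unpooled SE = √((0.1411 + 0.0778) / 250) = 0.02959. Φ[(0.085 − 0.05847) / 0.02959] = Φ(0.897) = 81.5%.
- 20% versus 10%, 200 per arm: Φ[(0.10 − 0.06998) / 0.03536] = Φ(0.849) = 80.2%.

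Both reproduce the claim.

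**Step 2. Formulas.** In each stratum there are n per arm, N = 2n, a apixaban events, c control events and m = a + c.
- Test: z = Σ(a − m/2) / √Σ[n²m(N − m) / (N²(N − 1))].
- Interval (assumed: usual Greenland-Robins log-scale variance): RR = R/S with R = Σan/N and S = Σcn/N; variance of log RR = Σ[(mn² − acN)/N²] / (RS).

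**Step 3. One stratum, 26/250 versus 41/250.**
- Test: null variance = 67 × 433 / (4 × 499) = 14.53; z = −7.5 / 3.812 = −1.967; one-sided p = 0.0246. Passes.
- Interval: RR = 0.634, log RR = −0.4555; variance = 1/26 + 1/41 − 2/250 = 0.05485, SE 0.2342; upper limit = exp(−0.4555 + 1.96 × 0.2342) = 1.004. Fails.

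The apixaban/control pairs 17/30, 21/35, 31/47 and 37/54 disagree in the same way.

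**Step 4. Two strata of 175 and 75 per arm, apixaban 18 + 8, control 21 + 20.**
- Test: variances 8.688 + 5.732 = 14.42; z = (−1.5 − 6) / 3.797 = −1.975; p = 0.0241. Passes.
- Interval: R = 13, S = 20.5, RR = 0.634; variance = 14.603 / 266.5 = 0.0548, SE 0.2341; limits 0.401 to 1.003. Fails.
- A test-based interval has upper limit exp[log RR × (1 − 1.96/|z|)], here 0.997. It is below 1 exactly when the test is significant.

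**Step 5. Frequency.** Exact enumeration of all one-stratum tables with 250 per arm:

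| True rates | Test passes | Interval passes | Test only | Interval only |
|---|---|---|---|---|
| 17% vs 8.5% | 82.1% | 81.4% | 0.69% | 0 |
| 20% vs 10% | 88.7% | 88.3% | 0.44% | 0 |
| 17% vs 11% | 49.2% | 48.2% | 0.94% | 0 |
| 5% vs 2.5% | 31.2% | 26.8% | 4.4% | 0 |
| 17% vs 17% (null) | 2.49% | 2.39% | 0.11% | 0 |

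Two-stratum simulation (1,000,000 trials per scenario; assumed 50%, 70% or 85% aged under 10, and an older-stratum rate 1 or 2 times the younger) barely changed this: about 0.65 to 0.7% at 17% versus 8.5%, and about 4.3% at 5% versus 2.5%. In a simulation at 17% versus 8.5% with a 70% share and equal stratum rates, discordant trials had p of about 0.023 to 0.025 and an upper limit of at most about 1.01.

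The same enumeration at 200 per arm and 20% versus 10% gives 80.7% by the test and 79.8% by the interval.

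**Step 6. Effect of the unstated formula at 17% versus 8.5%.** Disagreement is 0 with a test-based interval, about 0.7% with the usual interval, and about 2.4 to 5.3% with an inverse-variance (logit) interval. With a continuity-corrected CMH test and the usual interval it is about 3.1%.

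**Step 7. Tipping point.** At 250 per arm, the largest apixaban count still significant differs by one between the rules for 5 of the 30 control counts from 30 to 59. With 41 control events it is 26 by the test and 25 by the interval.

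**The case against.** The strongest reply is that SAP 7.5.1 does name a rule. A reader might infer two competing superiority criteria with nothing to choose between them. The text does not support that: the interval condition is mandatory, and the p-value is reported in addition. What remains is that SAP 7.5 and protocol 8.4.2 call the same interval descriptive, so the documents disagree about its role.

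A second reply is that the correspondence cannot be called false outright, because the variance is not stated and a test-based interval would make the sentence exactly true. That is right. The defect is an unspecified interval together with an equivalence that the usual choice does not have.

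A third reply is that the effect is tiny and conservative. At the design rates that stands. Rates could be lower than assumed, since SAP 7.5.1 counts subjects without imaging or a symptomatic event as event-free, but 5% versus 2.5% is an illustration, not a forecast.

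Finally, keeping the interval rule and deleting the equivalence sentence would also give a single criterion. It would, but it would leave the decision on a quantity that protocol 8.4.2 treats as descriptive.

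**Conclusion.** The point holds as a minor clarification. With the usual log-scale interval the equivalence in SAP 7.5.1 is not exact, and a result with p just under 0.025 can fail the interval by a hair. At 250 per arm this happens in about 0.7% of trials at 17% versus 8.5% and about 4% at 5% versus 2.5%.

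Three stronger readings should be resisted.
- A reader might infer a false-positive risk. Under the null at 17% the exact one-sided error is 2.49% by the test and 2.39% by the interval, so neither exceeds 2.5%.
- A reader might infer that the trial is underpowered under the interval rule. In the ITT scenario power is 82.1% or 81.4%, both above 80%. Only in the second scenario, after 20% exclusion, does the interval rule dip to 79.8%, and ITT, not that reduced set, is the primary population.
- A reader might infer that the interval is always stricter. That held in every scenario run here, but it is not a theorem: 179/260 versus 184/240 gives p = 0.0252 and an upper limit of 0.9999. Such rates are irrelevant to this trial.

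The results assume the usual Mantel-Haenszel log-scale variance and no continuity correction. Stratum shares and stratum rates are assumptions, and the results were insensitive to them.

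**What to change.** In SAP 7.5.1, state that superiority is declared if and only if the one-sided p-value from the age-stratified CMH test is below 0.025. This matches SAP 7.5 and protocol 8.4.2. State that no continuity correction is applied, if that is the intention.

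Then either delete the sentence claiming correspondence and leave the interval descriptive, with its formula named, or specify an interval that agrees with the CMH test at a relative risk of 1. A test-based interval does so, as does a stratified score interval with Mantel-Haenszel weights. The weights must be written down, because other weights can bring the mismatch back. The formula text should also say what is reported if the apixaban arm has no events, where the log-scale limit is undefined.

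In SAP 7.5.1.1, define significance in the tipping-point analysis by the same statistic in its non-stratified form.

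The cost is a few sentences in the SAP and possibly a different interval option in the program. Design, data collection and sample size do not change.

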- Venography – Venography may be performed when clinical suspicion for deep venous thrombosis is high, but ultrasound is negative or nondiagnostic. Installation of contrast into the vein (using the central line if a line study or another catheter) under fluoroscopy /digital subtraction angiography may show a thrombus.

Symptomatic DVT detected at any time during the study:

If a subject presents with signs and symptoms suggestive of a symptomatic DVT, conduct physical examination and perform diagnostic imaging tests within 48 hours of event. Specific recommendations are as follows:

- Conduct physical examination

- Treat for DVT per investigator standard of care (the American College of Chest Physicians evidence based clinical practice guidelines (9th Edition). may be used as a reference¹)
- Submit to the sponsor all relevant CRFs, clinical records and reports, CDs or DVDs of ultrasound, echocardiograms, venography, and other relevant information to support the diagnosis of a symptomatic DVT
- Report the DVT as an AE or SAE according to standard definitions and, if needed, clinical judgment

Asymptomatic DVT detected during the assessment period:

In the event that a DVT is incidentally detected while undergoing other imaging procedures required for the subject’s care of his/her underlying condition, and the subject does not manifest any signs or symptoms of a DVT, the event will be considered an asymptomatic DVT. The subject should be managed and further investigated according to the investigator’s standard of care. All diagnostic imaging tests should also be submitted for adjudication (CDs, DVDs, and reports). Specific recommendations are as follows:

- Conduct physical examination
- Treat for DVT per investigator standard of care (the American College of Chest Physicians evidence based clinical practice guidelines (9th Edition). may be used as a reference¹)
- Submit to the sponsor all relevant CRFs, clinical records and reports, CDs or DVDs of ultrasound, echocardiograms, line study, venography, and other relevant information to support the diagnosis of an asymptomatic DVT
- Report the DVT as an AE or SAE according to standard definitions and, if needed, clinical judgment

	Site	Likely clinical signs and symptoms	Diagnostic method/s
Cardiac	Right atrial	CVAD occlusion, sepsis, congestive heart failure	ECHO

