In the event that a PE is incidentally detected while undergoing other imaging procedures required for the subject's care of his/her underlying condition, and the subject does not manifest any signs and/or symptoms of a PE, the event will be considered an asymptomatic PE. The subject should be managed and further investigated according to the investigator's standard of care. All diagnostic imaging procedures performed such as CT pulmonary angiogram/VQ scan and US should also be submitted for adjudication as a suspected PE.

If a subject presents with an asymptomatic PE, specific recommendations are as follows:

- Conduct a physical examination
- Treat for PE per investigator standard of care (the American College of Chest Physicians evidence based clinical practice guidelines (9th Edition). may be used as a reference¹)
- Report as AE/SAE according to clinical judgment
- Collect relevant CRFs and reports to submit to the Sponsor
- Follow to resolution or stabilization
- Record as a suspected PE

Table 2: Evaluation and diagnosis for patients with suspected pulmonary embolism²			
	Site	Likely clinical signs and symptoms	Diagnostic method/s
PE	Pulmonary vasculature	Respiratory symptoms (dyspnea at rest or with exertion, pleuritic chest pain, hypoxia, cough, tachypnea), Respiratory signs (eg, tachypnea, tachycardia, loud P2) DVT source (eg, catheter thrombosis) Other: eg, syncope, “unexplained pneumonia, shock”	CT-PA V/Q scan (if low probability for PE, venography or compression US may be helpful) Pulmonary angiogram (Echocardiogram – less useful) (MR-PA – inferior to CT-PA)

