4 ENDPOINTS

4.1 Primary Endpoints

Efficacy:

The primary efficacy endpoint is a composite of adjudicated non-fatal DVT (including asymptomatic and symptomatic), PE, and CVST and VTE-related-death objectively confirmed by independent adjudication. All components of the primary efficacy endpoint will be adjudicated by a blinded, independent adjudication committee.

Safety:

The primary safety endpoint will be adjudicated major bleeding which is defined as bleeding that satisfies one or more of the following criteria: (i) fatal bleeding; (ii) clinically overt bleeding associated with a decrease in hemoglobin of at least 20g/L (ie, 2g/dL) in a 24-hour period; (iii) bleeding that is retroperitoneal, pulmonary, intracranial, or otherwise involves the CNS; and/or (iv) bleeding that requires surgical intervention in an operating suite, including interventional radiology. Of note, the major bleeding will not be considered as part of the primary endpoint for the purpose of the European application, but will be assessed as part of the safety profile of apixaban.

Prophylactic transfusions without overt bleeding and without a decrease in hemoglobin of at least 20 g/L (i.e., 2 g/dL) in a 24-hour period are not considered bleeding events.

All bleeding events will be adjudicated by a blinded, independent adjudication committee as major bleeding, CRNM bleeding, or minor bleeding. These endpoints are consistent with those recommended by the International Society on Thrombosis and Haemostasis for pediatric clinical trials in venous thromboembolism.

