6.3 Populations for Analyses

The following population will be used for the analyses.

Enrolled Population

The Enrolled Subjects population consists of all subjects who signed informed consent.

Randomized /Intent-To-Treat (ITT) Population

The Randomized/Intent-to-treat (ITT) population consists of all subjects who were randomized to a treatment, regardless of whether they received study drug or not. Except as noted otherwise, the ITT Population will be used for evaluation of efficacy.

Modified Intent-To-Treat (mITT) Population

The mITT population includes randomized subjects who have either an adjudicated event making up the primary efficacy endpoint or evaluable end of study imaging evaluations, including ultrasound and echocardiogram

Evaluable Population

The Evaluable population will include the Randomized/ITT population, except those subjects with relevant protocol deviations expected to affect the primary efficacy endpoint.

The relevant protocol deviations, used to determine exclusions, are listed in [Section 7.2](#).

Safety Population

The safety population for safety endpoints includes all randomized subjects, since there is no intervention on top of standard of care in the control arm. Additional analyses will be performed for subjects treated with apixaban.

Pharmacokinetic (PK) Population

The analysis population for pharmacokinetic assessments will include subjects who have received at least one dose of apixaban and have a pharmacokinetic sample collected.

Pharmacodynamics (PD) Population

The analysis population for anti-FXa assessments will include subjects who have received at least one dose of apixaban and have anti-FXa samples collected.

Subgroup Populations

Table 6.3-1 shows the subpopulations of interest for analyses of efficacy and bleeding.

Table 6.3-1: Subgroups of Interest for Efficacy and Bleeding Assessments

Grouping Variable	Subgroups
Geographic region	North America Europe Latin America Asia/Pacific
Age (stratification variable)	< 10 years old ≥10 to < 18 years old
Age category	Young Children 1 year to <2 years Young Children 2 years to 6 years Children 6 years to <12 years Adolescents 12 years to <18 years
Ethnicity	Hispanic/Latino

Table 6.3-1: Subgroups of Interest for Efficacy and Bleeding Assessments

Grouping Variable	Subgroups
	Not Hispanic/Latino
Gender	Male Female
Race	White Black / African American Asian Other
Weight	< 35 kg ≥35 kg

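### SAP 7.5.1's rule for unscanned children tests for a symptomatic event, so an adjudicated silent DVT or PE found only on another imaging method is scored as no event in the primary ITT analysis

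*SAP*

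**What the plan says.** **Endpoint.** SAP 4.1: "The primary efficacy endpoint is a composite of adjudicated non-fatal DVT (including asymptomatic and symptomatic), PE, and CVST and VTE-related-death". Asymptomatic DVT is included by name. PE and CVST carry no symptom condition.

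**Scoring rule.** SAP 7.5.1 repeats that the composite covers both asymptomatic and symptomatic DVT and puts the analysis on all randomized subjects. It then ends: "Subjects with no symptomatic event and no ultrasound or echocardiogram assessment will be counted as not having an event".

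**Silent events found by chance.** Protocol Appendix 3 provides for this: "In the event that a DVT is incidentally detected while undergoing other imaging procedures" needed for the child's care, where "the subject does not manifest any signs or symptoms of a DVT, the event will be considered an asymptomatic DVT". The images go to adjudication. Appendix 4 does the same for PE: "the event will be considered an asymptomatic PE", and the imaging "should also be submitted for adjudication as a suspected PE". The methods listed in these appendices go beyond ultrasound and echocardiography. They include CT and CT venography, MRI and MR venography, V/Q scanning, contrast venography and line studies.

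**mITT.** SAP 6.3 admits "randomized subjects who have either an adjudicated event making up the primary efficacy endpoint or evaluable end of study imaging evaluations". An adjudicated event is enough, with or without symptoms and with or without study scans.

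**Role of adjudication.** Protocol 7.2 states that the committee's results are the basis of the final primary analyses.

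**The concern.** The sentence in SAP 7.5.1 is meant to settle children whose outcome is unknown. Its wording also catches some whose outcome is known. A child whose silent clot was seen on CT and confirmed by the committee has had no symptomatic event. If neither an ultrasound nor an echocardiogram was done, both conditions of the sentence are met and the child is scored event-free.

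The ITT and mITT analyses would then differ on a confirmed outcome, when they should differ only in how they treat missing ones. The rule governs the trial's one confirmatory efficacy test, in an open-label study. An analyst would have to choose between the literal sentence and the endpoint definition with treatment assignment potentially known. The multiple-imputation and tipping-point analyses in SAP 7.5.1.1 deal with missing data and do not address this.

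**Working it through.** **1. The passages side by side.** Take a child with an adjudicated asymptomatic PE seen on CT during the Intended Treatment Period, with no ultrasound and no echocardiogram.

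| Text | How it treats this child |
|---|---|
| SAP 4.1, primary endpoint | Event: an adjudicated PE, with no symptom condition |
| Protocol Appendix 4 | A positive CT pulmonary angiogram is sufficient for a positive PE; the incidental silent case goes to adjudication |
| SAP 6.3, mITT | Included because of the event |
| Protocol 7.2 | Adjudicated result is the basis of the primary analysis |
| SAP 7.5.1, last sentence | No symptomatic event and neither scan: no event |

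The same holds for an asymptomatic DVT seen only on CT venography, MR venography, contrast venography or a line study. Neither SAP 7.5 nor Protocol 8.4.2 exempts adjudicated asymptomatic events, and the protocol gives no competing rule for unscanned children in the ITT analysis.

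**2. The plan's power figure.** Inputs from SAP 5: about 500 randomized 1:1, so 250 per arm; 17% v 8.5%; one-sided 0.025; Pearson chi-square.

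- Mean rate (0.17 + 0.085)/2 = 0.1275.
- Null SE = √(2 × 0.1275 × 0.8725 / 250) = 0.02983.
- Alternative SE = √((0.17 × 0.83 + 0.085 × 0.915) / 250) = 0.02959.
- z = (0.085 − 1.96 × 0.02983) / 0.02959 = 0.897, so power = 81.5%.

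Second scenario, 20% v 10% with 20% excluded (200 per arm): power = 80.2%. Both agree with the stated figure of more than 80%.

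**3. Size of the effect per child.** One rescored child changes an arm's rate by 1/250 = 0.4 percentage points. Expected events at the planning rates are 250 × 0.17 = 42.5 and 250 × 0.085 = 21.25.

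**4. Could one child matter?** These are illustrative counts, unstratified, 250 per arm. Upper 95% limit = RR × exp(1.96 × √(1/a − 1/250 + 1/b − 1/250)), with a apixaban and b control events.

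| Apixaban v control | RR | Upper limit | One-sided p |
|---|---|---|---|
| 21 v 43 (near plan) | 0.488 | 0.798 | 0.0016 |
| 20 v 43 | 0.465 | 0.767 | 0.0010 |
| 27 v 41 | 0.659 | 1.036 | 0.0339 |
| 26 v 41 | 0.634 | 1.004 | 0.0245 |
| 25 v 41 | 0.610 | 0.971 | 0.0173 |

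Near the planned rates, one rescored apixaban child changes nothing material. At counts chosen to sit on the boundary, one child moves the upper limit across 1 (26 to 25) or the p-value across 0.025 (27 to 26).

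**The case against.** The strongest reply is that the sentence, read in context, is only a default for unknown outcomes. Protocol 7.2 makes adjudication decisive. SAP 7.5.1 itself names asymptomatic DVT in the composite and compares proportions of subjects with primary endpoints. A sensible analyst would count the confirmed event. This shows the intent, and it stands as such. It does not amend the only explicit counting rule for unscanned children, and that rule gives the wrong answer when followed as written.

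The second reply is that the situation should hardly arise, and this largely stands. Protocol 3.5 and 5.1 ask for every attempt at ultrasound and echocardiogram within 72 hours of an event. A thromboembolic event requires stopping study drug, and the footnote to Table 5.1-2 requires early discontinuers to complete both scans. Also, the rule refers to ultrasound or echocardiogram in general, so a clot seen on a clinical ultrasound or echocardiogram falls outside it.

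A reader might infer three stronger points, which the documents do not support:

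- *Lacking either scan triggers the rule.* The ordinary sense is that neither was done. A child with an ultrasound has had an assessment.
- *Power falls below 80%.* That would need an assumed share of all events to be lost, and the documents give no such share.
- *Confirmed asymptomatic CVST is lost too.* Appendix 5 calls it an event and sends it to adjudication, but its positive classification requires symptoms as well as imaging. SAP 4.1 sets no such condition. Whether it counts is a separate inconsistency.

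**Conclusion.** The rule is wrong as written, with a small expected effect. It contradicts SAP 4.1 and the mITT definition for a narrow group: children with an adjudicated asymptomatic DVT or PE found only by a method other than ultrasound or echocardiography, who had neither of those scans. The number is not given and is probably very small, possibly zero; that judgement rests on the protocol's imaging requirements being followed. The sample size and stated power are unaffected. The boundary counts in the working are assumptions, chosen to show that a single child can decide the result, and do not forecast that one will. The reason to act is that a confirmatory rule should not leave the scoring of confirmed events to judgement at analysis.

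**What to change.** Replace the last sentence of SAP 7.5.1 with wording to this effect: *A subject is scored as event-free for lack of imaging only if no component of the primary efficacy endpoint was confirmed by adjudication, by any imaging method, within the Intended Treatment Period (including imaging up to Day 40 under Section 8.3), and neither an ultrasound nor an echocardiogram was assessed.*

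The period limit is needed. Protocol 5.4 sends suspected events for adjudication from consent to Day 35 ± 5, while SAP 6.1 bases efficacy on randomization through the Day 29 visit. Without the limit, events before randomization or in follow-up could be brought in.

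In the same revision, reconcile Appendix 5 with SAP 4.1 by stating whether an adjudicated asymptomatic CVST is a primary endpoint event.

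The cost is one sentence in the SAP plus that clarification. No new data are needed, and neither sample size nor alpha changes. It should be done before the treatment-group results are known.
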